### 5.1.3. Intra-Operative Exclusion Criteria

Subjects will be excluded from participating in this registry if any of the following exclusion criteria occur during the intravascular procedure, prior to enrollment (i.e., prior to insertion of VASCADE VCS):

Intra-Operative Exclusion Criteria	
 
1. Use of a final introducer sheath > 12 cm (or > 15 cm in overall length), or not 5, 6 or 7 Fr diameter;
 
2. Contralateral femoral arterial access with > 5 Fr catheter that is not successfully closed with a closure device during the index procedure
 
3. Index groin involves a previously placed permanent closure device (e.g., Starclose), where the device cannot be visualized to confirm that it is at least 1 cm proximal or distal to the puncture site;
 
4. Femoral artery diameter less than 6 mm at access site;
 
5. Angiographic evidence of moderate to severe calcium, > 50% stenosis, or a stent within 1 cm of the puncture site;
 
6. Overlapping Common Femoral Vein and Femoral Artery at access site;
 
7. Presence or placement of ipsilateral venous sheath during procedure;
 
8. Antegrade arterial access site: 
 
a. is a side stick
 
b. is NOT a single anterior wall femoral puncture
 
c. is NOT below the inguinal ligament / lower half of femoral head and NOT below the inferior epigastric artery origin from the external iliac artery;
 
 
 
9. More than one ipsilateral arterial access site is required in the index limb (e.g., femoral or other);
 
10. Intra-procedural bleeding around sheath, or suspected intraluminal thrombus, hematoma, pseudoaneurysm, or AV fistula;
 

---	---

	
11. Evidence of arterial insufficiency, emboli, or new stenosis / occlusion in the ipsilateral limb at the conclusion of the index intervention (i.e., complications occurring from untreated, or suboptimal treatment of disease);
 
12. Systemic hypertension (BP greater than 180/110 mmHg) or hypotension (BP less than 90/60 mmHg) just prior to enrollment;
 
13. Length of the tissue tract, the distance between the anterior arterial wall and skin, is estimated to be less than 2.5 cm;
 
14. If the physician deems that a different method should be used to achieve hemostasis of the arterial site;
 
15. Upon final angio/fluoro assessment of the final introducer sheath to be used for VASCADE delivery, documented evidence of:
 
a. inadequate sheath placement (e.g., location, position, angle), and/or
 
b. any kinking of the procedural sheath prior to enrollment and insertion of the VASCADE VCS.

--	---

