	
a hematocrit less than 30% based on institution's standard pre-operative lab values;
 
14. Renal insufficiency (serum creatinine of > 2.5 mg/dl);
 
15. Females who are pregnant, planning to become pregnant within 3 months of the procedure, or lactating;
 
16. Extreme morbid obesity (BMI greater than 45 kg/m^2) or underweight (BMI less than 20 kg/m^2);
 
17. Known allergy/adverse reaction to bovine derivatives;
 
18. Administration of low molecular weight heparin (LMWH) within 8 hours of the procedure.

Intra-Operative Exclusion Criteria
	
Subjects will be excluded from participating in this registry if any of the following exclusion criteria occur during the endovascular procedure, prior to enrollment (i.e., prior to insertion of VASCADE VCS):
 
 
1. Use of a final introducer sheath > 12 cm (or > 15 cm in overall length), or not 5, 6 or 7 Fr diameter;
 
2. Contralateral femoral arterial access with > 5 Fr catheter that is not successfully closed with a closure device during the index procedure;
 
3. Index groin involves a previously placed permanent closure device (e.g., Starclose), where the device cannot be visualized to confirm that it is at least 1 cm proximal or distal to the puncture site;
 
4. Femoral artery diameter less than 6 mm at access site;
 
5. Angiographic evidence of moderate to severe calcium, > 50% stenosis, or a stent within 1 cm of the puncture site;
 
6. Overlapping Common Femoral Vein and Femoral Artery at access site;
 
7. Presence or placement of ipsilateral venous sheath during procedure;
 
8. Antegrade arterial access site:       
 
a. is a side stick
 
b. is NOT a single anterior wall femoral puncture
 
c. is NOT below the inguinal ligament / lower half of femoral head and not below the inferior epigastric artery origin from the external iliac artery;
 
 
 
9. More than one ipsilateral arterial access site is required in the
 

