#### 5.1.1. Pre- Operative Inclusion Criteria

All subjects are required to meet the following inclusion criteria in order to be considered eligible for participation in this registry:

Pre-Operative Inclusion Criteria	
 
1. 18 to 80 years of age;
 
2. Capable and willing to give informed consent;
 
3. Acceptable candidate for an elective, non-emergent ipsilateral peripheral interventional endovascular procedure via antegrade access of the femoral artery using a 5, 6 or 7 Fr introducer sheath;
 
4. Acceptable candidate for post-procedural manual compression;
 
5. Able and willing to complete a follow-up office visit between 1-15 days post-procedure, and subsequent follow-up telephone assessment between 23-37 days;
 
6. Subject is able to ambulate at least 20 feet, with or without assistance (e.g., ambulatory amputee);
 
7. Acceptable candidate for emergent vascular surgery.
 

---	--

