### **7.2. Enrollment**

At the completion of the endovascular procedure, patients who meet all the pre- and intra-operative eligibility criteria may be enrolled in the registry and are eligible to receive the VASCADE VCS for access site hemostasis as part of the registry. The Investigator will acknowledge intention to enroll the patient prior to VASCADE VCS insertion into the procedural sheath, and it will be documented on a source worksheet. Once Investigator acknowledgement has been made and the device has entered the body, the subject is considered enrolled into the registry and should complete all evaluations and follow-up requirements. An Enrollment Notification eCRF must be completed and submitted within 24 hours to notify Sponsor of enrollment.

If a patient does not meet all eligibility criteria for the registry, the patient may receive one of the following to achieve arterial hemostasis, at the Investigator's discretion: 1) the VASCADE VCS as a commercial device, but the subject will not be enrolled in the registry; 2) another commercially available closure device; or 3) manual compression. These patients and the final reason for registry exclusion will be documented on the Screening/Enrollment Log.

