#### **14.3 Protocol Deviations**

A protocol deviation is defined as an event where the Investigator or site personnel did not conduct the registry according to the protocol.

Due to the post-market nature of this registry, no waivers will be granted for inclusion/exclusion criteria. Subjects who do not meet all criteria may be treated commercially with the VASCADE VCS at the Investigator's discretion, but shall not be enrolled in the registry.

Deviations must be reported to Cardiva Medical regardless of whether medically justifiable, pre-approved by Cardiva Medical or taken to protect the subject in an emergency. Protocol deviations will be reported on the Protocol

Deviation case report form. Investigators will adhere to procedures for reporting study deviations to their IRB in accordance with their specific IRB reporting policies and procedures.

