## PRECAUTIONS

- The VASCADE VCS should only be used by a trained licensed physician or healthcare professional.
  - Do not use in access sites where there is suspicion of a “backwall” stick. Increased bleeding risk may occur.
  - Do not use if arteriotomy is noted to be a “side stick.” Bleeding risk may increase.
  - Do not use if arteriotomy site is noted to be “high,” above the Inguinal Ligament (cephalad to lower half of the femoral head or the inferior epigastric artery origin from the external iliac artery). This may increase the risk of bleeding.
  - Do not use in an artery with suspected intraluminal thrombus, hematoma, pseudoaneurysm, or arteriovenous fistula. These conditions may complicate proper device use and performance.
  - Do not use if intra-procedural bleeding around the introducer sheath is noted including hematoma formation (sign of possible multiple wall stick). This may suggest problems with the access site.
  - Do not use in a procedural sheath > 12cm in length (or >15cm in overall length) or with a diameter other than 5F for VASCADE 5F, or 6F or 7F for VASCADE 6/7F. This may complicate disk deployment.
- 

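### Exclusion 8c joins the two high-puncture landmarks with *and* where the IFU joins them with *or*, so read literally it does not exclude a femoral puncture above the lower half of the femoral head but below the epigastric origin

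*Combined protocol and SAP*

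**What the plan says.** Section 5.1.3 lists the intra-operative exclusions, and any one of them is enough to exclude. Criterion 8 concerns the antegrade access site. Under 8c a site is excluded if it "is NOT below the inguinal ligament / lower half of femoral head and NOT below the inferior epigastric artery origin" from the external iliac artery. The Synopsis has the same rule with the same connector: "is NOT below the inguinal ligament / lower half of femoral head and not below the inferior epigastric artery origin".

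The IFU in Attachment 2 covers the same hazard under Precautions. It says not to use the device if the arteriotomy is high, meaning "above the Inguinal Ligament (cephalad to lower half of the femoral head or the inferior epigastric artery origin from the external iliac artery"), and gives the reason: "This may increase the risk of bleeding".

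Section 7.2 makes the written criteria the gate to the registry: "patients who meet all the pre- and intra-operative eligibility criteria may be enrolled in the registry and are eligible to receive the VASCADE VCS". Section 14.3 adds that "no waivers will be granted for inclusion/exclusion criteria". Section 1.1 states that data collection should be consistent with the IFU. Section 9.1.1 puts every enrolled subject who receives any part of the device in the ITT population. Section 9.1.2 puts those who have the collagen deployed and satisfy every inclusion and exclusion criterion in the Per Protocol (PP) population.

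**The concern.** The two rules use the same landmarks but different connectors. To be eligible, a site should be below both landmarks. The matching exclusion is a site that fails to be below one *or* fails to be below the other. The protocol negates each landmark but keeps *and*, which makes the exclusion narrower than the IFU precaution.

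At stake is which patients the registry describes. Bleeding events appear in both the major and the minor complication composites (Sections 8.3 and 8.4), and the IFU links a high site to bleeding. If sites read 8c differently, some could enrol punctures that others turn away. A PP analysis could also contain patients in whom the label advises against use, without any eligibility deviation being recorded.

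**Working it through.** No figure in the plan is involved, so the check sets the two rules side by side.

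Let A = the site is not below the first landmark (inguinal ligament / lower half of the femoral head), and B = the site is not below the second landmark (epigastric origin).

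- 8c, read literally: exclude if A **and** B.
- IFU precaution: do not use if the site is cephalad to the lower half of the femoral head **or** cephalad to the epigastric origin.

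| Site | Literal 8c | IFU precaution |
|---|---|---|
| Below both landmarks | not excluded | no objection |
| Above the lower half of the femoral head, below the epigastric origin | not excluded | do not use |
| Not above the lower half of the femoral head, above the epigastric origin | not excluded | do not use |
| Above both | excluded | do not use |

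The second row is the case that matters, because it can be a femoral puncture. It is below the epigastric origin, so B is false and *A and B* is false. That holds whatever value A takes, so the result does not depend on how the slash in the first landmark is read.

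The third row is a mismatch on paper only. The documents do not show whether such a position occurs, or whether other criteria would already remove it.

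Next, does anything else in the plan exclude the second-row case?

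- 8b excludes a site that "is NOT a single anterior wall femoral puncture". A single anterior-wall femoral puncture at this level passes.
- Inclusion 3 asks for a candidate for a procedure "via antegrade access of the femoral artery using a 5, 6 or 7 Fr introducer sheath". This patient meets it.
- Exclusion 14 (the physician prefers another method) and exclusion 15a (inadequate sheath placement on the final image) could stop the case. Both are eligibility criteria, but they rest on judgement and name no height landmark.
- Section 7.4.3 asks for deployment according to the IFU, and Section 15.4 lists failure to follow it among reasons to suspend a centre. Neither is an eligibility criterion.
- The IFU preparation step confirms a single-wall common femoral arteriotomy. It does not check height against the femoral head.
- Section 7.4.2 requires a contrast injection to verify the intra-operative criteria, but that verifies 8c as written.

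No other section restates 8c with *or*. A patient who gets past 14, 15a and IFU adherence therefore meets the criteria as written on this point and may be enrolled under Section 7.2. That patient enters ITT under Section 9.1.1, and PP under Section 9.1.2 once the collagen is deployed, provided the remaining criteria are met.

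**The case against.** The strongest reply is that 8c is only loosely worded. The IFU treats *high* as one concept, with the landmarks as ways of recognising it. The slash in 8c also runs ligament and femoral head together as one boundary. An investigator who reads 8c as not (below one and below the other) arrives at exactly the IFU rule, and Section 1.1 suggests that this was meant. The intent is probably as claimed. The wording does not carry it, because both versions repeat the negation before the second landmark.

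The safeguards are also real. The final angiogram is mandatory, the image is kept, 15a is itself an eligibility criterion and so also governs PP membership, and investigators are chosen for antegrade closure experience (Section 12.2). This lowers the chance that a gap case is enrolled. It does not make 8c say what the IFU says.

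It can further be argued that ITT is primary and is the same under either wording. That does not hold: a patient excluded before device insertion is never enrolled, so the wording affects ITT as well as PP.

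A reader might also infer more than the documents support:

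- **That 8c is redundant because 8b already removes everything it excludes.** This needs 8b and inclusion 3 to act as checks of vessel level. 8b can equally be read as a check of wall and number of punctures, and inclusion 3 is a pre-operative candidacy criterion.
- **That the gap can be given as a fraction of the high positions.** This would count rows of a logic table, not patients, and would depend on how the slash is resolved and on whether the third row occurs at all.
- **That the protocol directs use against a contraindication.** The IFU item is a precaution, and Section 7.4.3 still points to the IFU.

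**Conclusion.** The point holds as a minor wording error in an operative eligibility rule. Read literally, 8c is narrower than the IFU precaution and does not exclude a femoral puncture above the lower half of the femoral head but below the epigastric origin.

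The conclusion assumes the literal reading of the connector. If every investigator applies the IFU rule, the practical effect is nil. The documents give no frequency for this puncture level, and none is assumed. For scale only, at the full 100 subjects one patient is 1/100 = 1 percentage point of any reported proportion. The registry is descriptive and single-arm, with no hypothesis test, so no sample size or error rate is affected. The effect on the reported results is probably small.

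**What to change.** In both the Synopsis and Section 5.1.3, reword 8c to exclude a site that is high, in the IFU's own terms: "above the Inguinal Ligament (cephalad to lower half of the femoral head or the inferior epigastric artery origin from the external iliac artery"). Repeat *to* after *or*, so that either landmark is plainly sufficient.

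This is better than only changing *and* to *or*. Using *cephalad to* in place of the negated *below* keeps eligible a puncture level with the lower half of the femoral head, which the IFU does not call high. It also removes the ambiguous slash.

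The cost is one line in two places. Section 7.4.2 already requires the angiographic access-site assessment and the contrast injection that verifies eligibility, so no new procedure or eCRF field is needed. Enrolment is not narrowed beyond the existing IFU precaution.

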## 5.2. Withdrawal of Subjects

While withdrawal is discouraged, subjects may withdraw from the registry at any time, with or without reason and without prejudice to further treatment. In all cases of withdrawal, the reason(s) for withdrawal (if given) will be recorded upon registry termination.

In addition, the Investigator may withdraw the subject due to any reason determined by the Investigator to be in the best interest of the subject.

Subjects withdrawn from the registry prior to hemostasis (e.g., after enrollment and prior to deployment of the collagen plug) should be converted to conventional means (manual compression) to achieve hemostasis.

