#### 7.5. Follow-up

All enrolled subjects are required to complete an office visit between days 1-15, and a 30 (+/- 7) day telephone follow-up. Depending on each institution's

standard practice for follow-up visits, subjects may return to the office for access site assessment any time between 1 and 15 days post-procedure. The subject should be instructed that a follow-up telephone assessment will be conducted between day 23 and 37 to complete the study. It is important that all subjects are contacted within the 30 (+/- 7) day window to determine Procedural Success.

During both the office visit and telephone follow-up, the subject should be queried regarding any complications they experienced after hospital discharge and the status of the access site wound should be assessed. All subjects will be evaluated for symptoms of lower extremity neuropathy in the ipsilateral limb that were not existing prior to the index procedure (i.e., paresthesias, numbness, weakness), including an assessment of severity.

In the event of refusal to return to the clinic, a protocol deviation will be reported and a telephone follow-up will be completed.

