## **7.6. Study Exit**

Once the subject has completed the follow-up visit or has withdrawn, they should be exited from the registry provided they do not have any conditions that require continued follow-up. The date of exit and subject status will be recorded.

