## 9.2.2. Performance Outcomes

### 9.2.2.1. Primary Performance Outcome Analysis (TTH)

The primary performance outcome to be described is time to hemostasis (TTH) as defined in Section 8.1. Summary statistics for TTH (mean, standard deviation, median, minimum, and maximum) will be reported for the ITT and PP subject cohorts, and as described in Section 9.1. Ninety-five percent confidence intervals will be presented for means and medians. The proportions of enrolled Cardiva VASCADE™ VCS subjects converted to manual compression will also be reported.

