## 13.3. Registry Reporting Requirements for Adverse Events

The following adverse events must be reported in this post-market registry:

- serious, device-related adverse events (i.e., "reportable")
- major or minor access site closure-related complications (serious and non-serious), as defined in Section 8
- any adverse event that, in the Investigator's opinion, is clinically significant AND is any one of the following:
  - device-related
  - access site-related
  - access limb-related.

1. Complete an Adverse Event eCRF within 24 hours of knowledge of a reportable event. Medical records (e.g., procedure notes, operative notes, discharge summary, relevant progress notes, imaging or lab studies) may be requested by Cardiva Medical or its designee for event review and potential adjudication.

2. For questions, contact [name] at [contact].

All required adverse events (AE) (serious and non-serious) will be recorded on the eCRF and monitored from the time of enrollment through study exit.

In addition to 21 CFR 803 seriousness definitions, the following definitions for Serious Adverse Events will be used for consistency with published comparative data (per GCP, E6).

A serious adverse event (SAE) is defined as an event which leads to:

- Death due to any cause
- Life-threatening condition
- Results in persistent or significant disability/incapacity
- Requires in-patient hospitalization or prolonged hospitalization
- Necessitates an intervention to prevent a permanent impairment of a body function or permanent damage to a body structure
- Results in congenital abnormality

The following definitions for rating severity of adverse events will be used:

- Mild: Awareness of signs or symptoms, but easily tolerated; are of minor irritant type; causing no loss of time from normal activities; symptoms would not require medication or a medical evaluation; signs or symptoms are transient.
- Moderate: Interferes with the subject's usual activity and/or requires symptomatic treatment.
- Severe: Symptom(s) causing severe discomfort and significant impact of the subject's usual activity and requires treatment.

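### Section 5.2 does not separate stopping the device from withdrawing from the registry, so a failed closure can leave on day 0 without the 30-day complication follow-up

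*Combined protocol and SAP*

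**What the plan says.** Section 5.2 discourages withdrawal, but gives the Investigator a wide power: "the Investigator may withdraw the subject due to any reason determined by the Investigator to be in the best interest of the subject". It then deals with hemostasis in such cases: "Subjects withdrawn from the registry prior to hemostasis (e.g., after enrollment and prior to deployment of the collagen plug) should be converted" to manual compression.

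Section 7.6 exits a subject who "has withdrawn, they should be exited from the registry provided they do not have any conditions that require continued follow-up". Section 13.3 has the required adverse events "monitored from the time of enrollment through study exit". Section 9.1.3 rules out imputation.

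Other sections call for complete follow-up. Under 7.2, once the Investigator has acknowledged intent and the device is in the body, "the subject is considered enrolled into the registry and should complete all evaluations and follow-up requirements". Section 7.5 repeats the obligation: "All enrolled subjects are required to complete an office visit between days 1-15", followed by a telephone contact at day 23 to 37. Section 9.1.1 keeps everyone who received any part of the device treatment in the ITT population. Under 9.2.2.1 the proportion of enrolled "subjects converted to manual compression will also be reported". The footnote in 7.4.3 converts a subject with a suspected back-wall or secondary puncture to manual compression and does not mention withdrawal.

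**The concern.** Between device insertion and collagen deployment the patient is on the procedure table. An Investigator who withdraws a subject at that moment is, in practice, giving up on the device. Section 5.2 names this interval as its example and attaches to it the same action, manual compression, that 7.4.3 and the IFU attach to a failed closure. No section says that stopping the device is different from leaving the registry, or that a subject withdrawn by the Investigator is still contacted at 30 days.

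What is at stake is selective loss. Subjects whose closure failed may differ in risk from the rest, and the event that removes them is itself an outcome of the device. One site may apply 5.2 and 7.6 and another 7.2 and 7.5, so that the same failed closure is followed at one and not at the other. The composite of major complications is a primary outcome, and nothing in the analysis would recover an unobserved event.

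**Working it through.** **1. Two routes for the same failed closure**

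| Step | Conversion, no withdrawal declared | Investigator declares withdrawal |
|---|---|---|
| Source | 7.4.3 footnote, IFU steps | 5.2 |
| Hemostasis | Manual compression | Manual compression |
| ITT (9.1.1) | Included | Included |
| Day 1–15 visit and day 23–37 call (7.2, 7.5) | Required | Exited under 7.6 unless a condition needs follow-up |
| Adverse event monitoring (13.3) | To day 23–37 | To exit, possibly day 0 |

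The proviso in 7.6 protects a subject who already has a problem on day 0. It does not clearly protect one who is well that day and later has bleeding after discharge, an infection, or a nerve injury lasting more than 30 days. All of these are listed in 8.3 or 8.4.

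**2. Which outcomes are exposed**

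Device Success (8.2) needs collagen delivered, so a closure abandoned before deployment is a failure whatever happens later. Procedure Success in this registry needs Device Success, so it is also already a failure. That leaves the major (8.3) and minor (8.4) complication rates.

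**3. How many subjects (assumption: the pivotal retrograde trial's failure rates apply)**

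Inputs are from IFU Table 6. Its exact intervals reproduce: 128/136 gives 88.7–97.4% and 135/139 gives 92.8–99.2%.

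- Interventional failures: 139 − 135 = 4; 4/139 = 2.9% (exact 95% CI 0.8–7.2%).
- All failures: (136 − 128) + 4 = 12; 12/275 = 4.4% (2.3–7.5%).
- Expected per 100: about 3 to 4. Chance of at least one in 100: 1 − (1 − 4/139)^100 = 94.6%, or 98.8% at 12/275.
- The Table 6 footnote attributes 6 of the 12 to not following the IFU. Without these, success is given as 99% interventional and 98% overall, or about 1 to 2 failures per 100.

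These are failures of every kind. The documents do not say how many came before collagen deployment, nor how many an Investigator would label as withdrawals.

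**4. Effect on the major complication rate**

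The 95% Wilson limits are [p + z²/2n ± z√(p(1−p)/n + z²/4n²)] / (1 + z²/n), with z² = 3.8415. For zero events the upper limit reduces to z²/(n + z²).

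- 0/100, all followed: 3.8415/103.8415 = 3.70%.
- 0/96, four exited on day 0: 3.8415/99.8415 = 3.85%.
- 1/100, one event among the four and observed: 1.0% (0.18–5.45%).
- 4/100, the extreme in which all four had an event: 4.0% (1.57–9.84%).

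Four early exits cost 0.15 percentage points in the upper limit. One unobserved event changes the reported rate from 1% to 0%. Section 9.1.3 does not say whether exited subjects stay in the denominator, so the reported result could be 0/100 or 0/96.

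**5. What the prior data say about risk after failure**

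The pivotal trial had 0 major complications in 275 (IFU Table 1), so none among its 12 device failures. The Wilson upper limit for 0/12 is 3.8415/15.8415 = 24.2%. Twelve subjects neither show nor exclude a raised risk.

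**The case against.** A reader might infer that 5.2 defines abandoning the device as withdrawal. The text does not say that. The sentence starts from a subject already withdrawn and says how hemostasis is then obtained; it runs from withdrawal to conversion, not the reverse. Conversion without withdrawal is the documented pathway in 7.4.3 and in the IFU steps for disc pull-out and a visible marker stripe. Sections 7.2, 7.5, 9.1.1 and 9.2.2.1 treat such subjects as enrolled, followed and analysed. Day-0 exit therefore needs a separate best-interest withdrawal by the Investigator, in a protocol that discourages withdrawal, and the 7.6 proviso must not apply.

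The expected effect may also be small. The interventional figure is about 3 per 100, half of the prior failures involved not following the IFU, this registry uses experienced operators, and no major complication was seen in 275.

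All of this stands, and it limits the point to a gap in the wording. It does not close the gap. The Investigator's power is not restricted at device failure, the only example in 5.2 is that interval, and the proviso does not clearly reach late events in a subject who is well on day 0.

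**Conclusion.** The withdrawal and exit rules leave room for failed closures to be lost from the 30-day complication rates, against the follow-up that 7.2 and 7.5 require. The documents do not support saying that every abandoned device leads to exit, that these subjects drop out of ITT, or that the success endpoints are affected. A reader might also infer a large bias in the complication rates; the prior trial gives no evidence of one.

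The size rests on an assumption: failure rates from a retrograde-access trial, about 3 to 4 of any kind per 100, of which an unknown share would be withdrawn before collagen deployment. Loss of precision is trivial. The risk is that a single missed major event, in a registry of up to 100 where the prior trial saw none in 275, decides whether the primary rate reads 1% or 0%. The change is worth making because it costs almost nothing.

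**What to change.** State in 5.2 and 7.6 that conversion to another closure method, or an Investigator decision to stop using the device after it has entered the body, is not withdrawal from the registry. State that these subjects remain in ITT and complete adverse event reporting, the day 1–15 visit and the day 23–37 call unless they withdraw consent. Record conversion separately from Study Exit; the case report forms are not in the documents, so this may already be done.

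The Investigator's power to stop the device and the management of hemostasis are unchanged. The cost is wording in two sections, possibly one data field, and follow-up contacts for a few subjects that 7.2 already requires.
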